#### 6.3 Feasibility Considerations

In a recent internal Amgen study of the MarketScan® Early View database (Amgen Study 20200218), a total of 15212 erenumab-aooe users, 17239 users of other mAbs targeting the CGRP pathway, and 9242 users of onabotulinumtoxinA were identified from May 2018 through January 2020. In the same study, the rate of hypertension in new users of erenumab-aooe was 3.56 (95% confidence interval [CI]: 3.39, 3.73) per 10 PYs. In a separate study evaluating the rate of 19 vascular events in migraine patients, the rate of acute MI was 1.83 (95% CI: 1.78, 1.89) per 1000 PYs, the rate of ischemic stroke was 5.13 (95% CI: 5.04, 5.23) per 1000 PYs, and the rate of hemorrhagic stroke was 1.00 (95% CI: 0.95, 1.04) per 1000 PYs (Gill et al, 2020).

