#### Table 2. 95% CI Estimates and Half-widths for a Range of Cardiovascular Outcome Values, Based on a Sample Size of 20 000 Erenumab-aooe Users, 23 000 Users of Other mAbs Targeting the CGRP Pathway and 13 000 Onabotulinumtoxin A Users

	Erenumab-aooe N = 20 000		Other mAbs Targeting the CGRP Pathway N = 23 000		OnabotulinumtoxinsA N = 13 000	
CV Outcome (%)	95% CI	Half-width of Cl	95% CI	Half-width of Cl	95% CI	Half-width of Cl
0.20	0.14, 0.26	0.06	0.14, 0.26	0.06	0.12, 0.28	0.08
0.50	0.40, 0.60	0.10	0.41, 0.59	0.09	0.38, 0.62	0.12
1.00	0.86, 1.14	0.14	0.87, 1.13	0.13	0.83, 1.17	0.17
3.00	2.76, 3.24	0.24	2.78, 3.22	0.22	2.71, 3.29	0.29
5.00	4.70, 5.30	0.30	4.72, 5.28	0.28	4.63, 5.37	0.37
20.0	19.5, 20.6	0.55	19.5, 20.5	0.52	19.3, 20.7	0.69
30.0	29.4, 30.6	0.64	29.4, 30.6	0.59	29.2, 30.8	0.79

Abbreviations: CI: confidence interval; mAbs: monoclonal antibodies; CGRP: calcitonin gene-related peptide

Table 3 provides a range of detectable risk ratios for two outcomes of interest (acute MI and stroke), assuming 80% power, alpha-level of 0.05, and equal number of patients in each medication cohort, if a comparative analysis of the erenumab-aooe cohort to each comparator cohort (other mAbs targeting the CGRP pathway, selected SOC migraine preventive medications (anti-epileptics), or selected onabotulinumtoxinA ) were conducted. This table assumes a background rate of acute MI of 0.15 per 100 PYs and a background rate of stroke of 0.60 per 100 PYs (Gill et al, 2020).

 Table 3. Detectable Risk Ratios for Two Cardiovascular Outcomes

	Total Population in Each Medication Cohort						
Outcome	N = 13 000	N = 17 000	N = 20 000	N = 25 000			
Acute MI	2.10	1.94	1.85	1.75			
Stroke	1.58	1.51	1.46	1.41			

The estimates provided above are for informational purposes only. The final sample size for the study will change due to the criteria applied during the conduct of the protocol.

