### Decision to Proceed to Comparative Analyses

The decision to move forward with the comparative analysis for either the acute MI or the stroke outcome will be made after assessment of covariate balance across treatment groups (eg, based on an absolute standardized mean difference of > 0.10 for covariates included in the PS model, and adequate overlap in the PS across treatment arms), null findings for the final set of negative control outcomes (ie, posterior probability > 90% that the level of bias is less than 10% of the null), and sufficient sample size to detect a risk ratio of 2.0 or greater. For the relatively rate outcome of acute MI, a total of 15,000 patients in each comparator arm will be needed in order to detect a risk ratio of 2.0 or greater, assuming 80% power and a background rate of acute MI of 0.15 per 100 person-years. In contrast, for the outcome of stroke, 3,750 patients will be required in each treatment arm to detect a risk of 2.0 or greater, assuming 80% power and a background rate of stroke of 0.60 per 100 peson-years.

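### The patient-count thresholds for opening the MI and stroke comparisons, and the MI row of Table 3, hold only at about one person-year per patient, which the protocol neither states nor supports

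*Protocol*

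**What the plan says.** Protocol Section 8.7.2.4, Decision to Proceed to Comparative Analyses, makes one condition for starting a comparison "sufficient sample size to detect a risk ratio of 2.0 or greater". It turns this into patient counts. For acute MI, "a total of 15,000 patients in each comparator arm will be needed in order to detect a risk ratio of 2.0 or greater". The basis given there is power of 80% and an MI rate of 0.15 per 100 PY. For stroke, "3,750 patients will be required in each treatment arm to detect a risk of 2.0 or greater". The power is the same and the stroke rate is 0.60 per 100 PY.

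Section 8.5 (Study Size) gives detectable risk ratios in Table 3 from the same two background rates, "assuming 80% power, alpha-level of 0.05, and equal number of patients in each medication cohort". The MI row reads 2.10, 1.94, 1.85 and 1.75 for 13,000, 17,000, 20,000 and 25,000 patients per cohort. The stroke row reads 1.58, 1.51, 1.46 and 1.41. The table is labelled as informational; the decision rule in Section 8.7.2.4 carries no such label.

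No mean follow-up is given. Section 8.7.2.2 mentions only a maximum of about 2.5 years. Section 8.2.1 sets the study period at 17 May 2018 to 31 May 2020, or the latest data release. Section 8.7.2.4 plans risk ratios at 6 months, 1 year and 2 years. Section 8.2.5 defines an intention-to-treat follow-up and a per-protocol follow-up that ends at discontinuation or switching. Section 6.3 reports 15,212 erenumab users from May 2018 to January 2020, among whom "the rate of hypertension in new users of erenumab-aooe was 3.56 (95% confidence interval [CI]: 3.39, 3.73) per 10 PYs".

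**The concern.** Power for a rare outcome depends on events, and events depend on person-time. A rate in person-years gives a number of patients only once follow-up per patient is fixed, and the decision rule fixes none. If patients contribute well under a year on average, a comparison can pass the size criterion with far fewer events than a risk ratio of 2.0 requires.

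This matters because the count is a condition for opening a cardiovascular safety comparison. It is meant to keep uninformative comparisons closed, and as written it may not do so for MI.

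**Working it through.** **1. Reproducing the plan's figures.** Inputs: MI 0.15 and stroke 0.60 per 100 PY, risk ratio 2.0, 80% power, alpha 0.05 and equal arms (Sections 8.5 and 8.7.2.4). Sidedness is not stated; I take two-sided. With f person-years per patient, p0 = rate × f and p1 = 2 × p0. The arcsine formula is

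n per arm = (1.960 + 0.842)² / {2 × [asin√p1 − asin√p0]²}.

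At f = 1:
- MI: 3.924 / (0.05480 − 0.03874)² ≈ 15,215 (plan: 15,000).
- Stroke: 3.924 / (0.10976 − 0.07754)² ≈ 3,779 (plan: 3,750).

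Both thresholds imply the same expected events at f = 1: 15,000 × 0.0015 × (1 + 2) = 67.5 and 3,750 × 0.006 × 3 = 67.5. Schoenfeld's formula asks for 4 × 7.849 / (ln 2)² = 65.3, so 66 events.

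Solving the arcsine formula for the risk ratio at f = 1 gives the MI row of Table 3 exactly: 2.10, 1.94, 1.85, 1.75. The stroke row does not reproduce. At 0.60% it would be 1.50, 1.43, 1.39, 1.35. The printed values imply a comparator risk of about 0.44% to 0.45%, or about 0.75 PY at 0.60 per 100 PY.

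**2. What the plan suggests about f.**
- *6-month risk ratio:* f cannot exceed 0.5.
- *Feasibility rate (inference):* SE = (3.73 − 3.39)/3.92 = 0.0867 per 10 PY. Events ≈ (3.56/0.0867)² ≈ 1,685. Person-years ≈ 1,685/0.356 ≈ 4,730. Over 15,212 users this is 0.31 PY each (0.29 to 0.33 allowing for rounding of the interval). If 20% of users were excluded for baseline hypertension (assumption), 0.31/0.8 = 0.39; if 50%, 0.31/0.5 = 0.62. Reaching 1.0 needs about 69% excluded.
- *Administrative censoring only:* the 15% quarterly growth in Section 8.5 gives 15,212 × 1.15² ≈ 20,100, the projected 20,000. If that growth held since launch (assumption), λ = ln(1.15)/3 per month, T = 24.5 months, and mean follow-up is 1/λ − T·e^(−λT)/(1 − e^(−λT)) = 9.97 months, or 0.83 y. Over 30 months it is 0.97 y. Uniform entry over 24.5 months gives 24.5/2 = 12.25 months, or 1.02 y. All are before disenrolment.

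**3. Power for risk ratio 2.0** (two proportions, pooled variance, two-sided 5%; the arcsine formula gives at most about 1.5 points more):

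| f (PY) | Power at threshold (MI / stroke) | MI power at 20,000 per arm | MI detectable RR at 20,000 (arcsine) | MI patients per arm for 80% (arcsine) |
|---|---|---|---|---|
| 0.31 | 33% / 33% | 42% | 2.7 | 49,200 |
| 0.39 | 40% / 40% | 51% | 2.5 | 39,100 |
| 0.50 | 49% / 49% | 61% | 2.3 | 30,500 |
| 0.62 | 58% / 58% | 70% | 2.1 | 24,600 |
| 0.83 | 70% / 71% | 82% | 1.95 | 18,300 |
| 1.00 | 78% / 79% | 89% | 1.85 | 15,200 |

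**4. Stroke at projected sizes.** At 13,000 per arm, the smallest projected cohort, and 0.31 PY, power for risk ratio 2.0 is about 81%.

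**The case against.** One person-year is not impossible. Section 8.2.1 lets the data cut move, and administrative follow-up alone averages 0.97 to 1.02 y under the assumptions above. The thresholds could also be read as meant for the 1-year risk ratio. This stands as far as it goes, so 0.83 y must not be taken as a ceiling. But these averages precede disenrolment, the 1-year reading needs everyone followed for a full year, and neither helps the 6-month or per-protocol results.

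The feasibility figure is indirect, and this stands too. No person-years are reported. The 0.31 is back-calculated from a rounded interval in a separate study ending in January 2020, for a common outcome whose person-time may stop at the first event, exclude baseline hypertension or be on-treatment. A reader might infer that the plan's own data contradict one person-year. The documents support only that they do not back it.

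Four further readings go too far:
- *All of Table 3 assumes one person-year.* Only the MI row does.
- *Equal arms flatter the thresholds.* They are minimums per arm, so a larger second arm adds power. The projected 13,000 onabotulinumtoxinA cohort already fails the MI threshold.
- *Patients are counted before trimming.* The text does not say which count applies, and the decision follows the overlap assessment.
- *A null will be read as reassurance.* Nothing in the protocol says so, and results come with 95% confidence intervals.

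**Conclusion.** The point holds, mainly for MI. The counts of 15,000 and 3,750 and the MI row of Table 3 rest on about one person-year per patient, which the protocol does not state. At the 6-month time point, power at the threshold sizes cannot exceed about 50%; this needs no feasibility data. If mean follow-up is 0.31 to 0.62 PY, power is about 33% to 58%; at 0.83 PY it is about 70%. For MI at the projected 20,000 per arm, the criterion is met while the detectable risk ratio is about 2.7 at 0.31 PY and 2.3 at 0.5 PY, not 1.85.

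A reader might infer that the stroke comparisons are underpowered as well. At the projected sizes they are not; the stroke threshold misleads only if a cohort shrinks towards 3,750. Separately, the Table 3 stroke row and the abstract's 1.46 (a comparator risk near 0.45%) disagree with the stroke threshold (0.60%).

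These figures assume a two-sided 5% test, equal arms, the plan's background rates and no loss of precision from weighting. The follow-up values are scenarios, not data.

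**What to change.** In Section 8.7.2.4, replace the patient counts with one of the following, counted in the analysis set after trimming and separately for the intention-to-treat and per-protocol follow-up:
- about 66 to 70 events in both arms combined; or
- about 15,000 to 15,700 PY per arm for MI and 3,750 to 3,900 PY per arm for stroke. The lower figures are the plan's own counts at 1 PY, and the upper ones come from the pooled-variance formula (15,661 and 3,888).

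In Section 8.5, restate the MI row of Table 3 for a range of mean follow-up. By the arcsine formula above:

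| Mean follow-up | 13,000 | 17,000 | 20,000 | 25,000 |
|---|---|---|---|---|
| 0.3 y | 3.31 | 2.94 | 2.76 | 2.53 |
| 0.5 y | 2.67 | 2.42 | 2.28 | 2.12 |
| 0.8 y | 2.25 | 2.07 | 1.97 | 1.85 |
| 1.0 y | 2.10 | 1.94 | 1.85 | 1.75 |

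Reconcile the stroke row and the abstract's 1.46 with the stroke threshold, and state the risk and follow-up behind each. At 0.75 PY, which the printed row implies, the stroke threshold would be about 5,050 patients per arm rather than 3,750.

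The cost is one rewritten paragraph, one table and one abstract sentence. The detectable risk ratios become less favourable, and the MI comparisons may stay closed.

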### **Gated Analyses**

### Estimating the Cumulative Distribution of a Right-Censored Counterfactual Outcome

If appropriate based on comparability analyses, a comparison of the effect of erenumabaooe versus other mAbs targeting the CGRP pathway on acute MI at t=6 months, t=1 year, and t=2 years will be undertaken, where the effect measure of interest is the RR, and the possible sources of bias are confounding and dependent censoring.

First, to address confounding, let  $A_i$  be a discrete random variable denoting exposure to erenumab-aooe (a=1) or other mAbs targeting the CGRP pathway (a=0) for patient i,

and let  $T_i^a$  be the counterfactual time from medication initiation to the acute MI outcome for patient *i*. The counterfactual cumulative incidence of the outcome is then  $R^a(t) = \Pr(T_i^a < t)$ , and the estimate of the RR is:

$$RR(t) = \frac{R^1(t)}{R^0(t)}$$

To account for confounding we will use IPTWs, which will be constructed as follows:

$$\widehat{W}_i^1 = \frac{1}{\widehat{Pr}(A_i = a | L_i)}$$

For the analyses described here,  $Pr(A_i=a|L_i)$  is the conditional probability of treatment (ie, the propensity score described previously). The set of covariates comprising  $L_i$  are listed in Appendix D. The cumulative incidence curves for acute MI, weighted by IPTWs, now account for confounding by measured covariates, but still assume that censoring occurs at random. As previously noted, the risk ratio estimates and 95% confidence intervals at six months, at one year, and at two years will be presented; however, we are also interested in the entire cumulative incidence curve over time. The cumulative incidence curve will be presented graphically.

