Previous prophylactic treatment options for migraine have included anti-hypertensive drugs (eg, beta blockers and calcium channel blockers), anti-depressants (eg, tricyclics [TCAs], serotonin norepinephrine reuptake inhibitors [SNRIs], and selective serotonin reuptake inhibitors [SSRIs]), anti-epileptic medications (eg, topiramate), and botulinum toxins (indicated for the prevention of chronic migraine) (American Migraine Foundation, 2019; Estemalik et al, 2013; D'Amico and Tepper, 2008). All of these medications were originally developed for diseases other than migraine, but, more recently, two different classes of drugs blocking the calcitonin gene-related peptide (CGRP) pathway have been developed specifically for migraine: small molecule CGRP receptor antagonists (gepants) and monoclonal antibodies (mAbs), which either inhibit the canonical CGRP receptor or work by binding to the CGRP ligand (Deen et al, 2017).

The following four mAbs targeting the CGRP pathway have been approved for the prevention of migraine by the United States (US) Food and Drug Administration (FDA): erenumab-aooe (Aimovig®), fremanezumab-vfrm (Ajovy®), galcanezumab-gnlm (Emgality®), and eptinezumab-jjmr (Vyepti™). Erenumab-aooe was approved by the US FDA on 17 May 2018, followed by fremanezumab-vfrm on 14 September 2018,

galcanezumab-gnlm on 27 September 2018, and eptinezumab-jjmr on 21 February 2020.

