### 8.2 Setting and Study Population

### 8.2.1 Study Period

The study period will be from 17 May 2018, which is the date of US FDA approval for erenumab-aooe, to 31 May 2020 (or the latest release date for the MarketScan® claims database).

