## 8.7.2.2 Missing or Incomplete Data and Lost to Follow-up

This study is based on an analysis of automated medical and prescription claims data, and, because claims are collected for the purpose of payment, we assume that diagnoses and prescriptions reported in claims data are a true and accurate reflection of the health status, and medication and health service usage, for an individual. This will not always be true because individuals will sometimes not use medications as prescribed and will not report certain diagnoses. However, for the serious diagnoses, and related medication usage considered here, the presence of an associated claim will be interpreted as indicating that the procedure was conducted, the disease was present,

or the drug was consumed. The absence of a claim will indicate the opposite. As a result, when using claims data for research, missing data will be a concern mainly when lifestyle and biometrics are important for a given analyses because these items are not well captured in claims.

Patient demographics may be missing for a small subset of patients in claims data. Complete case analysis will be used when the overall missing observations (due to missing age and gender) is small. If a combination of these two covariates is missing for 5% or less of the study population, we will adopt a complete case analytic approach. An alternative solution that will be explored to account for the missing data is the use of inverse probability of missing weights, with one weight that would be estimated for missing age, and another weight that would be estimated for missing gender.

The MarketScan® claims database contains death information for a limited number of individuals who died in the inpatient setting. As a result, we assume that information on death is missing in MarketScan®. This missing data presents a challenge in observational studies with long follow-up, where competing risk by death might influence the study results. Our study, with a maximum possible follow-up of ~2.5 years, will be undertaken in a relatively young population, and we assume that the impact of competing risk by death will be minimal.

In claims data, loss to follow-up may occur as a result of plan disenrollment from the MarketScan® database. We will evaluate any loss to follow-up with descriptive statistics, and account for potential differential loss of follow-up with inverse probability of censoring weights.

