#### 8.7.2.3 Descriptive Analysis

### 8.7.2.3.1 Description of Study Enrollment

Selection of cohort members will begin by identifying all patients with at least one prescription order for erenumab-aooe, other mAbs targeting the CGRP pathway, selected anti-epileptic medications, and onabotulinumtoxinA, between 17 May 2018 through 31 May 2020 (or, the most recent data available in MarketScan®). Cohort members who meet the inclusion/exclusion criteria for the study will be included in the final analytic data files. Attrition for all four cohorts will be described in a flow chart (Figure 1).

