recipients), as this is stipulated by the federal government. This restriction of not allowing patients on government-funded health care programs to receive any financial assistance applies to all pharmaceutical companies, and, thus, patients on other mAbs targeting the CGRP pathway through government-funded health programs would also not be eligible to receive any financial assistance. As a consequence, the Marketscan® Medicaid Database provides an opportunity to indirectly evaluate the impact of the free drug and coupon programs on estimating risk amongst commercially insured patients, albeit in a study population that is potentially sicker and with higher levels of comorbidities. Through December 2019, there were 3181 new users of erenumab-acoe and 1692 new users of other mAbs targeting the CGRP pathway in the Marketscan® Medicaid Database. The expected number of new users through the administrative end of the study (31 May 2020) is: erenuamb ~ 4000; other mAbs targeting the CGRP pathway ~2500. We will estimate the cumulative incidence (ie, risk) of hypertension in both of these cohorts. Given the relatively small cohort sizes, estimation of the risk of rare outcomes such as acute MI and stroke will not be feasible. Comparative analyses will not be undertaken in the Marketscan® Medicaid Database.

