# Appendix D: *A Priori* List of Covariates to be Included in the Treatment and Censoring Modelsa

Footnotes defined on last page of table

Page 1 of 4

Characteristic	Treatment Model	Censoring Model	Numerical (N) or categorical (C)	Covariate assessment period*
Healthcare Utilization	Baseline period, Follow-up			
Ambulatory visits	Х	Х	N	
Emergency room visits	Х	Х	N	
Inpatient hospital visits	Х	Х	N	
Pneumococcal vaccination		Х	С	
Influenza vaccination		Х	С	
Herpes zoster vaccination		Х	С	
Eye exam		Х	С	
Screening colonoscopy		Х	С	
Screening PSA test		Х	С	
Screening fecal occult blood test		Х	С	
Screening mammogram		Х	С	
Oxygen equipment use		Х	С	
Home hospital bed		Х	С	
Mobility aids		Х	С	
Mechanical ventilation		Х	С	
Ambulance / life support		Х	С	
Rehabilitation services		Х	С	
Overall Medication Utilization	Baseline period, Follow- up			
Generic medications dispensed	X	Х	N	
Unique drug classes dispensed	Х	Х	N	

Footnotes defined on last page of table

Page 2 of 4

Characteristic	Treatment Model	Censoring Model	Numerical (N) or categorical (C)	Covariate assessment period*
Other Medications				Baseline Period
Contraceptives	Х	Х	С	
Anti-hypertensives	Х	Х	С	
Anti-coagulants	Х	Х	С	
Anti-platelets	Х	Х	С	
Lipid-lowering agents	Х	Х	С	
Anti-diabetics	Х	Х	С	
Cardiac glycosides	Х	Х	С	
Calcium gluconate	Х	Х	С	
Fludrocortisone/ Midodrine	Х	Х	С	
Weight loss prescriptions	Х	Х	С	
Fludrocortisone/ Midodrine	Х	Х	С	
Hyperpolarization-activated cyclic nucleotide-gated channel blocker	Х	X	С	
Comorbidities	I	1	1	Baseline Period
Diabetes mellitus	Х	Х	С	
Hypercholesterolemia	Х	Х	С	
Hypertension	Х	Х	С	
Liver disease / Cirrhosis	Х	Х	С	
Depression	Х	Х	С	
Chronic Obstructive Pulmonary Disease (COPD)	Х	X	С	
Renal Disease	Х	Х	С	
Cardiac arrhythmia	Х	Х	С	
Asthma	Х	Х	С	
Human immunodeficiency virus (HIV)	Х	Х	С	
Lupus	Х	Х	С	
Epilepsy/Seizure/Convulsions	Х	Х	С	
Anxiety	Х	Х	С	

Footnotes defined on last page of table

Page 3 of 4

Characteristic	Treatment Model	Censoring Model	Numerical (N) or categorical (C)	Covariate assessment period*
Comorbidities (continued)			Baseline Period	
Depression	Х	Х	С	
Peripheral Artery Disease	Х	Х	С	
Venous thromboembolism	Х	Х	С	
Critical limb ischemia	Х	Х	С	
Myocardial Ischemia	Х	Х	С	
Congestive heart failure	Х	Х	С	
Acute myocardial infarction	Х	Х	С	
Unstable angina	Х	Х	С	
Prinzmetal angina	Х	Х	С	
Other and unspecified angina pectoris	Х	Х	С	
Acute atrial fibrillation	Х	Х	С	
Paroxysmal atrial fibrillation	Х	Х	С	

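### The 2-year risk ratio of erenumab versus other CGRP mAbs has no comparator follow-up behind it at the named 31 May 2020 end date, and erenumab's 120-day head start is left unadjusted

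*Protocol*

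**What the plan says.** **Time points.** Section 8.7.2.4 plans, for erenumab versus the comparator, risk ratios on "other mAbs targeting the CGRP pathway on acute MI at t=6 months, t=1 year, and t=2 years will be undertaken". The same methods apply to stroke and to the contrasts with anti-epileptics and onabotulinumtoxinA. The descriptive part of that section also asks for cumulative incidence at 2 years.

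**End of data.** Section 8.2.1: "The study period will be from 17 May 2018, which is the date of US FDA approval for erenumab-aooe, to 31 May 2020". That sentence goes on to an alternative, "to 31 May 2020 (or the latest release date for the" MarketScan database, and Section 8.7.2.3.1 repeats it: "between 17 May 2018 through 31 May 2020 (or, the most recent data available in" MarketScan. Section 8.9.1.1 gives the date with no alternative: "The expected number of new users through the administrative end of the study (31 May 2020) is", followed by the Medicaid counts. The projections in Section 8.5 also run to 31 May 2020.

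**Length of follow-up.** Section 8.7.2.2 describes the study as one "with a maximum possible follow-up of ~2.5 years".

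**Drug availability.** Section 6.1: "Erenumab-aooe was approved by the US FDA on 17 May 2018, followed by fremanezumab-vfrm on 14 September 2018". Galcanezumab followed on 27 September 2018 and eptinezumab on 21 February 2020.

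**Calendar time.** Section 8.2.4 gives every cohort the same index window, the study period. Appendix D, the a priori "List of Covariates to be Included in the Treatment and Censoring Models", has no index date, quarter or year. Its footnote allows additions drawn from common diagnoses, procedures and medications. Index-date distributions appear only in Section 8.8, as a plausibility check.

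**The concern.** The comparator drugs came to market about four months after erenumab, and the named study period is barely two years long. A 2-year risk in the other-mAb arm therefore looks unobservable, although the plan promises a ratio and a 95% interval there. The estimator would not show the gap, because it can still return a number after the comparator arm has run out of follow-up. That number would tend to make erenumab look worse on myocardial infarction or stroke and could be read as a cardiovascular signal.

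A second issue follows from the same dates. In the first months after launch only erenumab users can enter the contrast with other mAbs. They have no contemporaneous comparator and also have the longest potential follow-up. Neither the index window nor the listed covariates deals with this.

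**Working it through.** **Inputs from the protocol.** Study start 17 May 2018 and named end 31 May 2020 (8.2.1). Approvals of other mAbs on 14 September 2018, 27 September 2018 and 21 February 2020 (6.1). Follow-up starts the day after index (8.2.5). Stroke background rate 0.60 and MI background rate 0.15 per 100 person-years (8.5). Erenumab users: 15,212 through January 2020, about 20,000 projected to 31 May 2020 (8.5).

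**1. The plan's own figure.** 17 May 2018 to 31 May 2020 is 365 + 366 + 14 = 745 days, and 745/365.25 = 2.04 years. The stated figure of about 2.5 years is not reproduced. Counting 2.5 years from 17 May 2018 gives an end at about 15 November 2020.

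**2. Longest possible follow-up at 31 May 2020.** These are upper bounds, taking approval as the earliest index date.

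| Drug | Earliest index | Days | Years |
|---|---|---|---|
| Erenumab | 17 May 2018 | 745 | 2.04 |
| Fremanezumab | 14 Sep 2018 | 625 | 1.71 |
| Galcanezumab | 27 Sep 2018 | 612 | 1.68 |
| Eptinezumab | 21 Feb 2020 | 100 | 0.27 |

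No other-mAb patient reaches 2 years. In the erenumab, anti-epileptic and onabotulinumtoxinA cohorts only those indexed from 17 to 31 May 2018 can. If accrual were uniform, that is 15/746 = 2.0% of erenumab users, about 400 of 20,000.

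**3. The later-release alternative.** The first possible 2-year comparator observation falls on 14 September 2020. Assuming uniform accrual from 14 September 2018 and no disenrollment:

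- End 30 September 2020: maximum 2.05 years; 16/747 = 2% of comparator patients can reach 2 years.
- End about 15 November 2020 (the 2.5-year reading): maximum 2.17 years.
- End 31 December 2020: maximum 2.30 years; 108/839 = 13% can reach 2 years.

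**4. What the estimator returns without support.** The weighted estimating function in Section 8.7.2.4 sums uncensored events before t. After day 625 no comparator event can be added, so the comparator risk stays at its 1.71-year value. With equal constant hazards (true ratio 1):

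- Stroke rate 0.006 per year: (1 − exp(−0.006 × 2)) / (1 − exp(−0.006 × 1.711)) = 0.01193/0.01021 = 1.17.
- MI rate 0.0015 per year: 0.002996/0.002563 = 1.17.

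**5. The head start.** 17 May to 14 September 2018 is 120 days (3.9 months). Under uniform accrual, 120/745 = 16% of erenumab users, about 3,200 of 20,000, enter before any comparator can. The protocol's counts suggest fewer: uniform accrual to 20,000 would give 624/745 × 20,000 = about 16,750 users by 31 January 2020, against the 15,212 reported, so entry is weighted towards later dates.

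**6. Whether the models pick this up.** Appendix D contains no calendar-time term. The censoring weights are specified for plan drop-out, switching and discontinuation. Administrative end of data, which depends directly on index date, is not among them. Propensity-score overlap cannot reveal a gap in a variable that the score does not contain.

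**The case against.** The strongest reply is that 31 May 2020 is not binding, since two sections allow the latest data release. The checklist in Appendix B is dated 23 March 2021 and Section 8.4 gives a claims lag of about 3 to 6 months. By inference, data to between late September and late December 2020 could have been available, and the figure of about 2.5 years would fit such a cut. This stands. A reader might infer that the 2-year ratio can never be estimated, or that 2.5 years is simply an arithmetic slip; the protocol supports neither without condition. But no later cut is fixed, and the 2-year support it would bring is thin.

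Next, the protocol nowhere says that the curve is carried flat, and the software might truncate it. That also stands: 1.17 is what the printed estimator implies, not a stated intention. A reader might also set 1.17 against the 0.91 to 1.10 band in Section 8.7.2.4. That band judges unmeasured confounding through negative control outcomes and is not a tolerance for extrapolation.

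On the head start, a reader might infer that positivity is violated or that much erenumab person-time precedes any comparator. Section 8.7.2.4 defines positivity over levels of the confounders, and nothing in the protocol links index date to MI or stroke risk. Under uniform accrual, person-time before 14 September 2018 is only (120²/2)/(745²/2) = 2.6% of the erenumab total. What remains certain is that early entrants lack contemporaneous comparators.

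Finally, at-risk thresholds and extra covariates are often left to a statistical analysis plan. Here, however, the protocol itself fixes the time points, the index window and the a priori covariate list.

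**Conclusion.** The point holds in conditional form. At the named end date, the 2-year risk ratio against other CGRP mAbs has no one at risk in the comparator arm (maximum 1.71 years), and in the other two contrasts it rests on patients indexed in about the first two weeks. The 31 May 2020 end date, the maximum follow-up of about 2.5 years and the 2-year time point cannot all stand and must be reconciled. A later cut rescues the 2-year comparison only past 14 September 2020, and then sparsely. The apparent ratio of 1.17 under no effect assumes equal constant hazards and a comparator curve left flat after 625 days.

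The 120-day head start is a fact at any data cut. The share of erenumab users affected is about 16% under uniform accrual and probably lower. Any bias from it depends on a relation between index date and outcome that the protocol does not quantify, so no size can be given. The 6-month and 1-year ratios are within the comparator's possible follow-up. The argument in Section 8.7.2.2 that competing death is minor is not weakened by a shorter maximum.

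**What to change.** - Name one data cut in Sections 8.2.1, 8.7.2.3.1 and 8.9.1.1, and make the maximum follow-up in Section 8.7.2.2 match it (2.04 years if the cut is 31 May 2020).
- At a 31 May 2020 cut, drop the 2-year risk ratio. At a later cut, report it only where both arms of the contrast keep adequate numbers at risk, by a threshold set in advance. Apply the same limit to the descriptive 2-year risks.
- For erenumab versus other mAbs, start the index window at 14 September 2018 in both arms.
- Add calendar quarter of index to the treatment and censoring models in Appendix D.

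The cost is protocol wording and one covariate derived from the index date, which is already in the data. The price is somewhat fewer erenumab users in the first contrast (at most about 16% under uniform accrual) and possibly no 2-year risk ratio.
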